Subjects showing clinical need for reinjection with IP between 12 to 16 weeks after the baseline injection visit in MP will continue treatment in OLEX with three injection sessions with injection intervals of  $14 \pm 2$  weeks in the same treatment combination chosen in MP but in injection doses of the high dose group of MP. The maximum total dose per injection session in OLEX is 500 U of NT 201 for subjects  $\geq 25$ kg BW and of GMFCS level I-III (see details on dose below and in [Section 8.1.1.2](#)).

A data monitoring committee [DMC] for the safeguard of subjects will monitor and assess adverse events [AEs], AEs of special interest [AESIs] and SAEs occurring after the injection treatment.

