### Duration of treatment per subject

The regular duration of study participation for subjects will be 50 to 66 weeks consisting of a screening period of 2 weeks followed by an observation period with 4 treatment cycles of 12 to 16 weeks each (total treatment period of 48 to 64 weeks).

Subjects not showing a clinical need for reinjection until 16 weeks after the baseline visit will end study participation after the final visit of MP without reinjection.

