### 7.2.1 Eligibility criteria for OLEX injections

Eligibility criteria will be assessed at the Final Visit of MP (V5) at  $14 \pm 2$  weeks after V2. In case the investigator is not certain when to schedule the Final Visit of MP at the Control Visit V4, 8 weeks after injection treatment in MP, the subject (if applicable) and/or parent(s) can be questioned at an optional TC (week  $12 \pm 3$  days) about the need for reinjection with IP. If this optional TC should indicate need for reinjection, the Final Visit of MP will be scheduled. If reinjection should not appear to be necessary at the time of optional TC Wk12, the Final Visit of MP could be scheduled until up to 16 weeks after V2 at the latest. If eligibility for reinjection should not be given up to 16 weeks after the previous injection, the subject will be withdrawn from the study (see [Section 7.4.1](#)). In OLEX, eligibility will be assessed at End of Cycle Visits V9 and V13.

 Menarche is defined as the 1st menstrual bleeding in female signaling the possibility of fertility (even if ovulation usually occurs only within some months after the menarche)

To qualify for reinjection in OLEX, per eligibility criterion No.1 all subjects in this study must have

- a) a clinical need for injection of the main clinical target patterns of UL(s) chosen at the Baseline Injection Visit V2 (i.e. either flexed elbow or flexed wrist alone or flexed elbow and flexed wrist) with fixed dose per pattern defined in [Table 14](#) **plus**
- b) a clinical need for the total dose of **8 U/kg BW NT 201** per UL (maximum dose of 200 U) per treated UL.

For the main clinical target patterns adaptations are only allowed within the dose ranges per muscle and number per injection sites given in [Table 14](#) as long as the total fixed dose per main clinical target pattern is kept.

For the remaining dose not used for treatment of main clinical target patterns of the UL(s) adaptations in OLEX may also include change of clinical target patterns and change of doses per muscles and number of injection sites as long as the ranges of [Table 14](#) are kept.

In subjects with additional treatment of LL(s) in treatment combinations B. – E. the clinical need must be for

- a) unilateral or bilateral treatment of LL(s) as chosen at the Baseline Injection Visit V2.
- b) The total dose of the treatment combination chosen at V2 (see also eligibility criterion No.2 below).

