3 CLINICAL STUDY DESIGN AND OBJECTIVES

3.1 Clinical Study Design

This is a prospective, multicenter, multi-national, randomized, double-blind, parallel-group, dose-response study in phase 3 of three doses NT 201. Subjects with upper limb spasticity alone or with combined upper limb (UL) and lower limb (LL) spasticity due to cerebral palsy (CP) will be treated. The study comprises a Main Period (MP) with a single double-blind treatment cycle with three dose arms (high, mid, low), followed by three open-label extension (OLEX) treatment cycles with a single treatment arm using the high dose regimen of MP. Each of the four treatment cycles has an observation period of 12 to 16 weeks, i.e. 14 weeks \pm 14 days.

Treatment of UL(s) in MP will be administered in three parallel dose groups of NT 201 with fixed doses to UL(s):

- In the high dose group 8 U/Kg BW NT 201 (maximum dose per UL: 200 Units (U) for subjects \geq 25kg BW).
- In the mid dose group 6 U/kg BW (maximum of 150 U) per UL.
- In the low dose group 2 U/kg BW (maximum of 50 U) per UL.

As clinically needed, UL treatment can be administered unilaterally or bilaterally and subjects may receive additional Botulinum Toxin (BoNT) injections in one out of five predefined treatment combinations (A-E) up to the maximum total dose applicable for their Gross Motor Function Classification System expanded and revised version (GMFCS-E&R) level (I-III: 20 U/kg BW NT 201, maximum of 500 U; IV and V: 16 U/kg BW NT 201, maximum of 400 U):

- Treatment Combination A: Unilateral or bilateral UL treatment only
- Treatment Combination B: Unilateral UL and unilateral LL treatment
- Treatment Combination C: Unilateral UL and bilateral LL treatment in GMFCS-E&R level I-III
- Treatment Combination D: Unilateral UL and bilateral LL treatment in GMFCS-E&R level IV-V
- Treatment Combination E: Bilateral UL and bilateral LL treatment in GMFCS-E&R level I-III

In MP only, LL(s) treatment will be performed within the same dose groups as UL treatment, i.e. subjects in the mid and low dose group will receive 75% or 25%, respectively, of the dose in the high dose group to all limbs treated.

A total of 344 subjects (2 : 1 : 1 ratio) will be enrolled with:

- At least 172 subjects randomized to the high dose group.
- At least 86 subjects to the mid dose group.
- At least 86 subjects to the low dose group.

The study includes the following visits:

Screening:

Screening Visit (V1): Day -14 (Week -2) ± 5 days

Main Period (MP):

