7.5.2 Secondary Safety Variables

Adverse events

AEs will be coded according to the Medical Dictionary for Regulatory Activities (MedDRA, version 21.0). For MP, only treatment emergent adverse events (TEAEs) of the MP will be analyzed, which are defined as AEs with onset or worsening on or after date and time of the first MP administration and before date and time of the first OLEX administration at V6. For subjects who do not receive an OLEX administration all AEs with onset or worsening on or after date and time of the first MP administration will be considered as TEAEs of MP. TEAEs of the OLEX are defined as AEs with onset or worsening at or after date and time of the first OLEX administration at V6. TEAEs will be allocated to an injection cycle x in the OLEX Period, if adverse events has onset or worsening on or after injection x and before injection x+1 (if applicable). TEAEs of the OLEX will be analyzed in total and per treatment cycle. Additionally TEAEs of the MP and the OLEX period will be displayed together in total.

Only TEAEs will be analyzed. Non-TEAEs will only be listed.

If an AE worsens between start and end of this AE it will be considered as new AE starting with the date of the worsening. In this case the imputation of end dates within episodes of the

same AE will be done by setting the end date/end time to start date/start time of the consecutive worsening record.

In detail missing or partially missing start and stop dates of an AE will be imputed as follows for the calculation of the duration of an AE:

- if start time is missing and start date is given and not equal to date of an injection visit, set start time to 00:00, else if start date is equal to date of an injection visit set start time to time of injection, if given (else 00:00)
- if start date/time is completely missing and end date is before first exposure in the MP: no imputation
- if start date/time is (partially) missing and end date after or equal first exposure in the MP or missing:
 - only start day is missing, but start month and start year same as an injection visit: set start day and start time to day and time of this injection visit, else set start day to 1 and start time to 00:00
 - start day and start month are missing, but start year is the same as year of first exposure in the MP: set start day, start month, start time to day, month, time of first exposure in the MP, else set start day and start month to 1 and start time to 00:00

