 - start date/time completely missing and end date/time not before date/time of first exposure in the MP, set start date/time to date/time of first exposure in the MP
 - if AE end date and time are missing set end date to study end date (i.e. last contact or last visit of the study) and end time to 23:59
 - if AE end date/time is partially missing, set end day to last day of the given month or end day/month to 31/12 of the given end year and missing end time to 23:59
 - if AE end time is missing set time to 23:59.

Imputation rules for multiple records in case of AE worsening:

- For missing AE start date/time the imputation strategies as defined above will be applied to all records of the same AE.
- For missing TEAE end date/time the imputation strategies as defined above will be applied to the last record of the same TEAE.

Calculation of time to onset/duration of AEs [days]:

- Time to onset of an AE is defined as start date of AE - date of most recent administration of study drug [+ 1 for AE starting after start of treatment]
- The duration will be calculated as stop date - onset date + 1 for each episode of worsening.

Incidences will be calculated for TEAEs overall (MP+OLEX), overall OLEX and by injection cycle on the system organ class (SOC) level and on the preferred term (PT) level (i.e., total, by worst intensity, by worst relationship, and by worst outcome). Listings and, if applicable, tables displaying incidences for TEAEs leading to discontinuation, serious TEAEs, related serious TEAEs, TEAEs of special interest, and deaths will also be provided. Additionally the number and percentage of subjects with at least one non-serious TEAE with incidence $\geq 5\%$

in any MP treatment group or in the OLEX Period and number of non-serious TEAE will be displayed by SOC level and PT level. Time to onset and duration of AEs will be listed. Time to onset and duration of AEs will be listed.

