The injection visit will be regarded as start of a cycle and the day before the next injection (or the last available visit in case of a discontinued cycle or the last cycle) will be regarded as end of cycle. Length of injection cycle and observation period in weeks will be calculated as follows:

- Total observation period in weeks over the entire study will be calculated as date of last available study visit (e.g. V17 for completers) - date of baseline visit V2 +1 day.
- Observational period of the MP in weeks will be calculated as:

Date of first injection in the OLEX V6 - date of baseline visit V2, if V6 is available.

Date of last available visit of the MP (e.g. V5 for completers of the MP) - date of baseline visit V2 +1 day, if V6 is not available.
- Observational period of the OLEX in weeks will be calculated as date of last available visit of the OLEX (e.g. V17 for completers) - date of first injection in the OLEX V6 +1 day.
- The injection cycle length of injection cycle (x) in weeks will be calculated as
 - Date of injection cycle (x+1) - date of injection (x) **or**
 - Date of last available visit – date of injection (x) +1 day in case of last or discontinued cycle

If injection cycle was not performed length of injection cycle will be missing.

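### Main-period adverse events are shown by dose as crude incidences over a window that ends partly on need for re-injection, so observation length may differ by arm

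*SAP*

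**What the plan says.** SAP 7.5.2 opens the main-period TEAE window at the first main-period injection and closes it for events "and before date and time of the first OLEX administration at V6". Subjects who are never re-injected have no stated closing day: "For subjects who do not receive an OLEX administration all AEs with onset or worsening on or after" the first main-period injection count.

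Re-injection timing depends on the subject. The protocol synopsis (Study design) sends into the extension "Subjects showing clinical need for reinjection with IP between 12 to 16 weeks after the baseline injection visit in MP". Protocol 7.2.1 allows an optional Week 12 telephone call to ask about need. If there is none yet, "the Final Visit of MP could be scheduled until up to 16 weeks after V2 at the latest". The synopsis (Duration of treatment per subject) adds: "Subjects not showing a clinical need for reinjection until 16 weeks after the baseline visit will end study participation" after the final main-period visit. SAP 3.1 confirms the range: "Each of the four treatment cycles has an observation period of 12 to 16 weeks".

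On the measure, SAP 7.5.2 says: "Incidences will be calculated for TEAEs overall (MP+OLEX), overall OLEX and by injection cycle", by system organ class and preferred term. SAP 7.5 asks for results by main-period treatment group as well as in total. SAP 7.6 derives the length of the main period for each subject ("Date of first injection in the OLEX V6 - date of baseline visit V2, if V6 is available", otherwise to the last available main-period visit). It summarises that length descriptively by treatment group. Nothing in the available text connects it to the adverse-event tables.

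**The concern.** Follow-up that ends on need for re-injection is, in part, a consequence of treatment response. If time to renewed need differs by dose, the arms are observed for different average times. A crude proportion with at least one event then mixes event rate with length of observation. Events unrelated to treatment, such as intercurrent infections, accumulate with time, so the arm observed longer would show more of them even at identical risk.

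This matters because the main period is the only randomised comparison of doses: everyone in the extension receives the high-dose regimen. Protocol 4.2 and 4.3 say that no randomised paediatric data and no monitored paediatric experience exist for this preparation. The by-arm tables will therefore be read for dose-related safety although no test is planned.

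**Working it through.** **1. The plan's own figure.** Study duration rests on the same cycle length: 2 + 4 × 12 = 50 weeks and 2 + 4 × 16 = 66 weeks, which matches the stated 50 to 66 weeks. None of the stated powers depends on the adverse-event window.

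**2. Bounds on the window.** The final main-period visit is Day 99 ± 14, so Day 85 to Day 113, or 12 to 16 weeks after Day 1. For subjects who keep to schedule, windows can differ by a factor of at most 16/12 = 1.33. Days 1 to 84 are common to all of them.

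**3. Size of the artefact.** The documents give neither event rates nor window lengths by arm, so both are assumptions and are shown as ranges. Let p be the 14-week incidence and give both arms the same constant hazard:

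- h = −ln(1 − p)/14
- incidence over t weeks = 1 − exp(−h·t)

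Each arm's mean window is used as if it applied to every subject in that arm.

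Example: p = 30% gives h = 0.3567/14 = 0.02548. At 13.5 weeks incidence is 1 − exp(−0.3439) = 29.1%. At 14.5 weeks it is 1 − exp(−0.3694) = 30.9%. The spurious difference is 1.8 points.

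| 14-week incidence | 13.5 vs 14.5 weeks | 13 vs 15 weeks | 12 vs 16 weeks |
|---|---|---|---|
| 10% | 0.7 | 1.4 | 2.7 |
| 30% | 1.8 | 3.6 | 7.1 |
| 50% | 2.5 | 5.0 | 9.9 |

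Entries are percentage points, from unrounded values. The last column needs every subject in one arm to stop at 12 weeks and every subject in the other at 16, which will not happen.

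**4. Rare events.** For p = 2%, h = 0.0202/14 = 0.001443. A 1-week difference gives 2.07% − 1.93% = 0.14 points, about 0.0014 × 172 = 0.24 of one subject in the high-dose arm.

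**5. Early events.** Let the hazard decay with half-life L weeks. With k = ln 2/L, the cumulative hazard is c(1 − exp(−k·t)), and c is set to reproduce p at 14 weeks. For p from 10% to 50%, even 12 against 16 weeks adds at most 0.4 points when L is 1 to 2 weeks, and 0.7 to 2.4 points when L is 4 weeks.

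**6. After the change.** With equal hazards, a common 12-week cut-off gives a spurious difference of zero at any rate. Events per unit of subject-time also give zero if the hazard is constant.

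**The case against.** A reader might infer that the higher dose lasts longer, is therefore watched longer, and will look less safe. The documents do not support that as a statement of fact. Protocol 6.2 treats duration of effect by dose as something the study will learn about; it gives no expected difference. The direction is also open. Protocol 6.1 (Revisit for reinjection) has a subject withdrawn when the investigator does not expect the criteria to be met by Week 16. A durable responder may therefore leave before Week 16, which shortens that window. Infection at the injection area, a positive pregnancy test or lack of agreement can also postpone or prevent re-injection, and the regular visit is at Week 14 whatever the dose.

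Other parts of the case against also stand. Safety analyses are descriptive, with no between-dose test. SAP 7.6 tabulates observation length and classified cycle length by treatment group, so an imbalance would be visible. Onset times are listed. Protocol 8.2.6 places signs of toxin excess within 12 to 72 hours of exposure, well inside the common period. The artefact is small beside sampling error: at 30% incidence, the 95% half-width for 172 against 86 subjects is 1.96 × √(0.21/172 + 0.21/86) = 11.9 points. Counting events from one injection to the next is a coherent attribution rule, and the SAP also uses it for the extension cycles. An exposure-adjusted table in Appendix 1 cannot be ruled out.

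These arguments limit the point but do not remove it. A reader who sees unequal mean windows cannot correct preferred-term incidences from them.

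**Conclusion.** The point holds in a limited form and is minor. The TEAE window closes partly on need for re-injection, observation length may therefore differ by arm, and the available SAP text makes no allowance for this in the by-arm incidences. For common background events (30% to 50% by 14 weeks) the artefact is about 1.8 to 2.5 points for a 1-week difference in mean window and 3.6 to 5.0 points for 2 weeks. It is about 0.7 points for a 1-week difference at 10% incidence, and negligible for rare events and early toxin effects. The 7 to 10 points in the extreme column should not be quoted as a realistic risk. All of these sizes rest on an assumed constant hazard, equal in both arms, and on assumed rates and window lengths. Neither the existence of an imbalance nor its direction can be established from the documents.

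**What to change.** For the main-period by-arm presentation of TEAEs, related TEAEs, TEAEs of special interest and serious TEAEs:

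1. Add a table of events with onset on Days 1 to 84 and designate it as the common-window dose comparison. The final main-period visit falls on Day 85 at the earliest, so every subject on schedule is covered. Early discontinuation remains and should be footnoted.
2. Give rates per subject-time by arm, using the main-period observation period from SAP 7.6 and counting only onsets inside that period.
3. Keep the full-window table.

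If Appendix 1 already contains such tables, a cross-reference in SAP 7.5.2 is enough. The cost is a few extra tables from data already collected. The 12-week table omits later events, but these remain in the full-window table.

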### 4.3 Risk-benefit assessment

There is no monitored experience in children/adolescents available for the BoNT-A preparation under investigation. NT 201 was subject to extensive toxicological and safety pharmacological testing in non-clinical as well as clinical studies, which showed that NT 201 is well tolerated and has an acceptable safety profile (see current IB [[Merz Pharmaceuticals \(GmbH\) - IB](#)]). In a juvenile toxicity study in rats, decreased mating rates and atrophy of the testicular germinal epithelium with subsequent hypospermia without functional consequences were observed at 30 Lethal Dose 50 (LD50) Units [LD50U]/kg. However, no indications of frank systemic toxicity other than growth retardation were seen at 10 LD50U/kg and below. The clinical relevance of the findings from this animal study with these extremely high doses and reinjection already at

maximal paralysis is unknown. In a clinical setting, subjects are only re-injected upon recovery of the muscle function, usually 3 to 6 months after injection of BoNT-A. In this study investigators who are informed on preclinical safety data of NT 201 will judge the clinical need for an injection in doses of up to a maximum of 20 U/kg BW NT 201 at least 12 weeks after the last injection treatment. Two clinical studies with NT 201 in adult subjects with UL muscle spasticity after stroke and other etiologies with a maximum dose of 400 U NT 201, respectively, showed good efficacy and no safety issues [Barnes 2010, Kanovsky 2011].

In general, BoNT-A is well tolerated in children/adolescents [Naumann and Jankovic 2004, Lukban 2009, Heinen 2010]. Common undesirable effects after BoNT-A injection include local, generalized, or procedural AEs. Local AEs are usually mild and self-limiting. The most commonly reported local AEs after BoNT treatment in children/adolescents are potential and expectable consequences of overshooting muscle relaxation such as excessive localized weakness [Love 2010]. Systemic AEs related to BoNT-A include nausea, fatigue, bladder incontinence, flu-like symptoms, and rash [Naumann 2006, Howell 2007]. Procedural AEs include complications due to local anesthesia or analgosedation before injection.

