## 7.3 Removal of subjects from treatment or assessment

### 7.3.1 *Discontinuation of subjects*

In accordance with the Declaration of Helsinki and the IC form, the subject or parent(s) may discontinue the study at any time without any penalty or loss of benefits to which the subjects is otherwise entitled (see [Section 7.4.3](#)). Both the discontinuation of study and the reason(s) why the study was prematurely discontinued must be recorded in the subject's file and the eCRF. Date and discontinuation circumstances should be stated. Further details on discontinuation could be documented in the respective section of the "End of Study" form of the eCRF.

Subjects must be discontinued from the study by the investigator at any time for any of the following reasons:

- Withdrawal of IC.
- Treatment with any other IP in another clinical study.
- Treatment with any BoNT other than study medication.
- Pregnancy (no further administration of IP(s), blood draw, or any other interventional procedure will be performed; see [Section 10.4](#)).
- Any AE for which treatment continuation would constitute an unacceptably high risk for the subject.
- AESIs of severe intensity that represent respiratory function disorders or swallowing disorders will trigger the premature termination of a subject without re-exposition to IP. The terms for these severe AESIs are:
  - AESI terms related to respiratory function disorders are aspiration, diaphragmatic paralysis, dyspnoea, pneumonia aspiration, respiratory arrest, respiratory depression, and respiratory failure.
  - AESI terms related to swallowing disorders are bulbar palsy, multiple cranial nerve palsies, dysphagia, hypoglossal nerve paresis, cranial nerve paresis, cranial nerve paralysis.
- Injection treatment cannot be performed for any reason, not even with local anesthesia and/or analgosedation.
- Eligibility criteria are not met after the previous injection of IP in the respective treatment cycle (MP or OLEX) (see [Section 7.3.1](#)).

The DMC may recommend further criteria for discontinuation. Deviations from this study protocol, or conditions comprising exclusion criteria established in [Section 7.3](#) that arise after the subject has been included in the study may (but will not necessarily) lead to the discontinuation of subject's study participation. All such conditions must be properly documented.

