### **8.2.3 Selection and timing of doses for each subject**

The investigator will decide with his/her experience-based judgment in botulinum toxin treatment of CP in conjunction with considering the AS in the target joints, whether treatment of the subject within specified dose limits and treatment patterns in this study is appropriate.

The investigator will assess the current clinical pattern of spasticity of UL(s) and LL(s), if applicable, and will decide which muscles require treatment with BoNT. The investigator will define one UL at the Screening Visit that will serve for (primary) efficacy analyses throughout MP and OLEX. In accordance with inclusion criteria, the AS score of all treated clinical patterns of spasticity including the main clinical target patterns (either flexed elbow or flexed wrist) must be  $\geq 2$  at the Baseline Injection Visit V2.

If the contralateral UL is also treated, secondary efficacy analyses in the main clinical target pattern(s) of this limb also will be performed. Allowed adjustments will help tailoring the NT 201 treatment to the individual condition of a subject by deciding on the treated clinical patterns, the dose per selected muscles and the number of injection sites. Details of the treatment are described in [Section 8.1.1.2](#).

After the screening period, IP will be injected once at the Baseline Injection Visit (V2) of the double-blind MP and up to three times in OLEX, if eligibility criteria for reinjection are met up to 16 weeks after the previous injection (for details on eligibility criteria see [Section 7.3.1](#)).

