#### **Adverse events**

Analyses of adverse events will be performed for total dose group in addition to total population and MP treatment group. AEs will be coded by system organ class and preferred term level according to the MedDRA version in effect at the time the respective databases of MP and of OLEX Period, respectively, are closed. Only TEAEs will be analyzed. Non-TEAEs are defined as baseline complaints and will be listed only.

For MP, only TEAEs of the MP will be analyzed, which are defined as AEs with onset or worsening on or after date and time of the first MP administration and before date and time of the first OLEX administration at V6. For subjects who do not receive an OLEX administration all AEs with onset or worsening on or after date and time of the first MP administration will be considered as TEAEs of MP.

-AEs starting in MP and not having resolved at the Final Visit V5 of MP will be followed and further documented during OLEX.

For OLEX period, only TEAEs of the OLEX will be analyzed, which are defined as AEs with onset or worsening on or after date and time of the first OLEX administration at V6. Frequencies will be calculated for TEAEs on the system organ class level and on the preferred term level. For all TEAEs the occurrence, worst intensity, final causal relationship to treatment assessed by investigator, and final outcome will be summarized by counts and percentages for all visits and overall. Listings and, if applicable, tables displaying frequencies of TEAEs leading to discontinuation, TESAEs, TEAESIs, and deaths will also be provided.

Additional subgroup analyses (e.g., classes for GMFCS level, age groups, use of anesthesia/analgo-sedation for injection treatment) will be specified in detail in the SAP.

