#### **12.4.7.5      *Examination of subgroups***

Subgroup analyses will be performed for the AS regarding treatment group, site (or pooled sites), BoNT-A pre-treatment status, GMFCS level groups at baseline, and AS baseline value. In addition, subgroup analysis for the AS regarding subjects with unilateral and bilateral treatment will be performed. If applicable, the influence of these subgroups will also be analyzed for the other efficacy variables. Potential effects of the use of local anesthetics and/or analgosedation on AS and adverse event/adverse events of special interest will be analyzed descriptively.

Details of subgroup analyses and additional subgroup analyses (e.g., gender, dose group, age, group [2-5, 6-11, 12-17 years], weight, height) will be specified in detail in the SAP.

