7.7.5 Examination of Subgroups

Subgroup analyses will be performed for the AS regarding treatment group, pooled sites, BoNT-A pre-treatment status, GMFCS-E&R level groups at Screening, AS baseline value, age (2-5, 6-11, 12-17 years), weight group at baseline (<25 kg, \geq 25 kg), use of local anesthetics and/or analgosedation and unilateral versus bilateral treatment. Shift tables and frequency tables of changes will not be presented for subgroup analyses.

Subgroup analysis for TEAEs, related TEAEs, serious TEAEs and TEAEs of special interest by SOC and PT will be performed for the following subgroups: GMFCS-E&R level groups, age (2-5, 6-11, 12-17 years), weight group at baseline (<25 kg, \geq 25 kg), and use of local anesthesia/analgosedation for injection treatment.

The following TEAESIs will be analyzed by UL treated, LL treated, not applicable (not located at any treated limb):

- Muscular weakness

- Monoparesis
- Hemiparesis
- Paralysis
- Paralysis flaccid
- Paraparesis
- Paresis
- Peripheral nerve palsy
- Peripheral paralysis
- Quadriparesis

For this analysis “UL treated” means that the AE is located at an upper limb, which was treated. “LL treated” means that the AE is located at a lower limb, which was treated. “Not applicable” means that the AE is not located at any treated limb.

For the subgroup analysis ‘use of local anesthetics and/or analgosedation’ the two following subgroups will be analyzed:

- Subjects with use analgesics and/or sedatives been used during corresponding injection
- Subjects without use analgesics and/or sedatives been used during corresponding injection

For the subgroup analysis regarding ‘unilateral versus bilateral treatment’ the following subgroups will be defined for analysis of the AS score of the ULs:

- Unilateral treatment of the upper limbs (Treatment combination A if unilateral, B, C and D)
- Bilateral treatment of the upper limbs (Treatment combination A if bilateral and E)

For analysis of the AS score of the LLs the following subgroups will be analyzed:

- Unilateral treatment of the lower limbs (Treatment combination B)
- Bilateral treatment of the lower limbs (Treatment combination C, D and E)

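### The sedation subgroup AE tables use TEAEs only, so a V2 sedation complication timed before the injection, with no later worsening, is listed but not tabulated

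*SAP*

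**What the plan says.** - **Aim.** Protocol 12.4.7.5: "Potential effects of the use of local anesthetics and/or analgosedation on AS and adverse event/adverse events of special interest will be analyzed descriptively".
- **Known procedural risk.** Protocol 4.3: "Procedural AEs include complications due to local anesthesia or analgosedation before injection".
- **What is tabulated.** SAP 7.5.2: "Only TEAEs will be analyzed. Non-TEAEs will only be listed". The main-period window runs from the V2 injection, by date and clock time, up to the V6 injection. Protocol 12.4.5 has the same rule and gives the excluded events a label: "Non-TEAEs are defined as baseline complaints and will be listed only".
- **How the sedation question is analysed.** SAP 7.7.5: "Subgroup analysis for TEAEs, related TEAEs, serious TEAEs and TEAEs of special interest by SOC and PT will be performed". Use of local anaesthesia/analgosedation is one of the subgroups named there, and the sedated group is defined as "Subjects with use analgesics and/or sedatives been used during corresponding injection".
- **Number of main-period injections.** Protocol 8.2.3: "IP will be injected once at the Baseline Injection Visit (V2) of the double-blind MP".

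**The concern.** A window that opens at the injection suits the question of what the study drug may have caused. It suits the question of what sedation may have caused less well, because sedation is already under way when the needle goes in. The events most closely tied in time to sedation can then fall just outside the window, in the group the table is meant to describe.

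At stake is the fairness of one descriptive comparison in children aged 2 to 17. Only sedated children can have a sedation complication, so leaving some out moves the comparison one way, towards no effect of sedation. Such events can be serious: under Protocol 10.2, an event during or after analgosedation that leads to an overnight stay counts as an SAE.

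**Working it through.** No figure in the plan depends on this window, so the check follows the rules case by case.

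**Inputs**
- TEAE window, handling of worsening, and start-time imputation: SAP 7.5.2.
- AE classes in the sedation subgroup: SAP 7.7.5 (four classes, all treatment-emergent).
- Timing of sedation: Protocol 8.3.1 allows it on injection days once the assessments are finished; Protocol 8.1.1.2 gives its purpose as easing the injection. It therefore starts before the injection.
- AE collection: from consent (Protocol 10.1), so pre-injection events are in the database.
- Required AE items: Protocol 10.1 names a date of onset but no time, although SAP 7.5.2 works with start times.

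**Trace of a sedation complication**

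| Case | Result |
|---|---|
| V2, timed before injection, no later worsening | Non-TEAE: listed only, absent from all four subgroup tables |
| V2, timed before injection, worsens afterwards | The worsening is a new AE and counts as a TEAE |
| V2 date, no time recorded | Start time set to injection time. TEAE if that rule, written for AE duration, also governs TEAE status; the SAP does not say |
| V2, onset at or after injection | TEAE |
| V6, before injection | TEAE of the main period, because that window closes only at the V6 injection |
| V10 or V14, before injection | TEAE of the preceding OLEX cycle |
| Sedated at V2 but not injected | Outside the main-period SES (SAP 5), so in no main-period safety table |

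Only the first case is a clear omission from the sedated subgroup. In the V6, V10 and V14 cases the event is counted, but the corresponding injection in SAP 7.7.5 could mean the one that opened the period or the one about to be given. If it means the former, a child unsedated at V2 who has a pre-injection complication under sedation at V6 is counted as unsedated.

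**Direction.** Let S be the number of sedated children, c those counted in a given table row, and m those whose only event for that row is of the first kind. The table shows c/S instead of (c + m)/S, a shortfall of m/S, which cannot be negative. The unsedated rate has no shortfall from this source.

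**Scale per child.** The documents give neither S nor m. As an illustration, take the planned 344 children and assume 25%, 50% or 75% are sedated at V2:
- 25%: S = 86, and 1/86 = 1.16 percentage points
- 50%: S = 172, and 1/172 = 0.58 points
- 75%: S = 258, and 1/258 = 0.39 points

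These are upper bounds per omitted event for these values of S, because a child who already has another TEAE in the same row is counted anyway. Fewer than 344 treated children would raise them slightly.

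**The case against.** The strongest reply is that the SAP does what the protocol asks. Protocol 12.4.5 limits AE analysis to TEAEs and, in the same text, announces the anaesthesia/analgosedation subgroup for the SAP to specify. On that reading sedation use divides up the post-injection AE profile, as GMFCS level and age do, and counting procedural complications is a different question. This stands to the extent that no protocol commitment is broken. It does not remove the mismatch with Protocol 12.4.7.5, which asks about effects of sedation itself.

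Other replies also have weight. The TEAE definition is standard and correct for its purpose. In Protocol 4.3, the words on timing may describe when sedation is given and not when the complication occurs. AESIs are defined in Protocol 10.3 as events after treatment, so the TEAESI table loses nothing that belongs in it. AEs are asked about 30 minutes after injection (Protocol 9.1.1.6), non-TEAEs are listed, and all SAEs go to the DMC. A listing, however, gives no comparison by sedation use.

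Three stronger inferences are not supported:
- A reader might conclude that the main-period tables can hold no pre-injection complication of V2 sedation at all. The imputation of untimed injection-day events may bring some in, and later worsening is counted.
- A reader might say that all 344 V2 sessions are affected. That says only that every treated child has a V2; only sedated children with an event of the first kind are affected.
- A reader might take "Injection treatment cannot be performed for any reason, not even with local anesthesia and/or analgosedation" in Protocol 7.3.1 to describe injections abandoned under sedation. It says that injection is not possible, and does not say that sedation had been started.

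**Conclusion.** The point holds, narrowly. A V2 sedation complication with a recorded pre-injection onset and no later worsening is left out of the sedated subgroup's AE tables, and this can only lower that subgroup's rate. How often it happens cannot be calculated: the documents give no rate for such events, no sedated share, and no indication of how often onset time is recorded. Many sedation complications, namely those starting or worsening at or after injection, are still counted. The analysis is descriptive and sedation is not randomised, so no dose comparison and no confirmatory test is affected. This is an optional, low-cost improvement and not an error in the TEAE rules.

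The conclusion assumes that TEAE status follows the recorded clock time where there is one. The SAP's appendix of tables and listings was not in the text reviewed, so it could not be checked for an output of this kind.

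**What to change.** Leave SAP 7.5.2 and every TEAE and TEAESI table unchanged, and move no event between periods. Add to SAP 7.7.5:

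1. One descriptive table of all AEs, treatment-emergent or not, with onset on the date of an injection visit, by visit (V2, V6, V10, V14) and by sedation/anaesthesia use at that same visit. The denominator is the subjects injected at that visit.
2. A separate listing of any AE in a child who was sedated but not injected.

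Because the table works by date, it does not depend on whether onset time was recorded or how it was imputed. Taking sedation use from the same visit also settles which injection corresponds for these events.

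The cost is one table, one short listing and a sentence or two of text. AE start date, injection date and sedation use per injection are already used in the SAP. Same-day events unrelated to sedation will also appear; the unsedated column shows that background. The comparison remains non-randomised and descriptive. The documents do not say whether sedation is recorded when no injection follows, so the listing may be incomplete.
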